### **10.3.6 Pregnancy**

#### **10.3.6.1 Maternal exposure**

If a patient becomes pregnant during the course of the study, the IPs should be discontinued immediately.

Pregnancy itself is not regarded as an AE unless there is a suspicion that the IP under study may have interfered with the effectiveness of a contraceptive medication. Congenital abnormalities or birth defects and spontaneous miscarriages should be reported and handled as SAEs. Elective abortions without complications should not be handled as AEs. The outcome of all pregnancies (spontaneous miscarriage, elective termination, ectopic pregnancy, normal birth, or congenital abnormality) should be followed up and documented even if the patient was discontinued from the study.

If any pregnancy occurs in the course of the study, then the Investigator or other site personnel should inform the appropriate AstraZeneca representatives within 1 day, i.e., immediately, but **no later than 24 hours** of when he or she becomes aware of it.

Clinical Study Protocol  
Investigational Drug Substance: MEDI4736  
Study Number **ESR 15 11078**  
Edition Number **1.09**  
Date **01 Feb 2018**

The designated AstraZeneca representative will work with the Investigator to ensure that all relevant information is provided to the AstraZeneca Patient Safety data entry site within 1 to 5 calendar days for SAEs and within 30 days for all other pregnancies.

The same timelines apply when outcome information is available.

#### **10.3.6.2 Paternal exposure**

Male patients should refrain from fathering a child or donating sperm during the study and for 90 days after the last dose of durvalumab monotherapy.

Pregnancy of the patient's partner is not considered to be an AE. However, the outcome of all pregnancies (spontaneous miscarriage, elective termination, ectopic pregnancy, normal birth, or congenital abnormality) occurring from the date of the first dose until 90 days after the last dose should, if possible, be followed up and documented.

Where a report of pregnancy is received, prior to obtaining information about the pregnancy, the Investigator must obtain the consent of the patient's partner. Therefore, the local study team should adopt the generic ICF template in line with local procedures and submit it to the relevant Ethics Committees (ECs)/Institutional Review Boards (IRBs) prior to use.

## **11. STATISTICAL METHODS AND SAMPLE SIZE DETERMINATION**

### **11.1 Statistical analysis plan summary**

This study will test the early toxicity and efficacy of durvalumab 1500 mg (or 20 mg/m^2) IV Q4W and RT to 2 separate lesions in metastatic pancreas cancer patients who have progressed through first-line chemotherapy. Radiation will be given to the same total dose (24 Gy) over 3 fractions to each lesion. This is a single-arm phase II trial with continuous monitoring of acute non-hematologic toxicity with the primary endpoint of progression free survival. Efficacy will be evaluated by time to progression or death, whichever comes first, and compared to historical control of chemotherapy alone as reported in the literature.

While the safety profile of durvalumab has been established when giving the drug as a single agent, the safety of combined durvalumab with ionizing radiation needs to be established. In case the defined boundary for the incidence of severe acute non-hematologic toxicity is crossed, the trial will be stopped, and the available data at that point will be carefully reviewed in order to suggest potential modification of the drug-radiation combination that may warrant testing in a future independent trial.

## 11.2 Statistical analysis plan

### 11.2.1 Continuous toxicity monitoring in the first 20 patients enrolled (stopping rule)

Continuous toxicity monitoring will occur for the first 20 patients enrolled. The endpoint is severe (G3-5) acute non-hematologic toxicity. G3-5 non-hematologic occurs in <10% of patients treated with the anti-PD-1/PD-L1 mAb alone (Robert, Ribas et al. 2014). Early stopping for unexpected, severe early toxicity is based on continuous monitoring of G3-5 toxicity with the aim of keeping the probability of early stopping at around 5% if the true underlying rate of this toxicity is 10%. Following Ivanova et al. (Ivanova, Qaqish et al. 2005), we use the boundary proposed by Pocock (Pocock 1977). Values of  $b_k$  for the current design are given in Table 1.

Table 1. Pocock boundary for early stopping due to grade 3+ toxicity with a probability of stopping of about  $\phi = 0.05$  and assuming the true toxicity rate is  $\theta_0 = 0.1$

k	1	2	3	4	5	6	7	8	9	10	11	12	13	14	15	16	17	18	19	20
<math>b_k</math>	–	2	3	3	3	3	4	4	4	4	4	4	5	5	5	5	5	6	6	6

It is important for the validity and practical implementation of this strategy that the sequence of patients entered into the study is strictly recorded and preserved. Ideally, the design assumes that the outcome, i.e. the incidence of G3+ toxicity among the first  $i$  patients is known when entering patient  $i+1$ . The accrual rate is expected to be around 1-2 patients per month and the time window for observing early toxicity in a patient is pragmatically defined as the time during and within two weeks after the completion of RT; therefore, insisting on complete observations before entering the next patient will slow down accrual considerably. Instead we will allow staggered entry of cases. For patient safety reasons, no more than 6 patients will be allowed to be on active treatment at any point during the continuous toxicity monitoring portion of the trial.

If the boundary is crossed, the treatment with durvalumab and RT will be discontinued in all patients on treatment at that point in time.

If 20 patients are enrolled and have completed therapy without crossing the toxicity boundary, the continuous toxicity monitoring component will be concluded and the outcome will be reported. Accrual will be continued with respect to the phase II efficacy question, although toxicity will still be recorded and reported for the whole phase II cohort.

The chosen design parameters for the continuous toxicity monitoring portion of the trial have been chosen to give a high probability of stopping the study in case of unexpectedly high risk of toxicity. The probability of early stopping is 4.9% if the true incidence of G3+ toxicity is 10%; the probability of early stopping is >99% if the true incidence of G3+ toxicity is 50% or more.

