#### Continuous toxicity monitoring in the first 20 patients enrolled (stopping rule)

The endpoint is severe (G3-5) acute non-hematologic toxicity. G3-5 non-hematologic occurs in <10% of patients treated with the anti-PD-1/PD-L1 mAb alone (Robert, Ribas et al. 2014). Early stopping for unexpected, severe early toxicity is based on continuous monitoring of G3-5 toxicity with the aim of keeping the probability of early stopping at around 5% if the true underlying rate of this toxicity is 10%. Following Ivanova et al. (Ivanova, Qaqish et al. 2005), we use the boundary proposed by Pocock (Pocock 1977). Values of  $b_k$  for the current design are given in Table 1.

Table 1. Pocock boundary for early stopping due to grade 3+ toxicity with a probability of stopping of about  $\phi = 0.05$  and assuming the true toxicity rate is  $\theta_0 = 0.1$

k	1	2	3	4	5	6	7	8	9	10	11	12	13	14	15	16	17	18	19	20
<math>b_k</math>	–	2	3	3	3	3	4	4	4	4	4	4	5	5	5	5	5	6	6	6

It is important for the validity and practical implementation of this strategy that the sequence of patients entered into the study is strictly recorded and preserved. Ideally, the design assumes that the outcome, i.e. the incidence of G3+ toxicity among the first  $i$  patients is known when entering patient  $i+1$ . The accrual rate is expected to be around 1-2 patients per month and the time window for observing early toxicity in a patient is pragmatically defined as the time during and within 2 weeks after the completion of RT; therefore, insisting on complete observations before entering the next patient will slow down accrual considerably. Instead we will allow staggered entry of cases. For patient safety reasons, no more than 6 patients will be allowed to be on active treatment at any point during continuous toxicity monitoring of the first 20 enrolled patients.

If the boundary is crossed, the treatment with durvalumab and RT will be discontinued in all patients on treatment at that point in time.

If 20 patients are enrolled and have completed therapy without crossing the toxicity boundary, this component of the trial will be concluded and the outcome will be reported. Accrual will be continued with respect to the phase II efficacy question, although toxicity will still be recorded and reported for the whole phase II cohort.

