### **5.2.2 Technical Factors**

Only photon therapy is permitted and energies  $\geq 6\text{MV}$  are required. Cobalt-60, electron, and charged particle therapies are not permitted. Treatment for each lesion should begin on a Monday and finish on a Wednesday when possible. RT is scheduled to be delivered daily on Days 15-17 and Days 29-31.

Because multiple lesions will sequentially receive RT, multiple isocenters should be used with each centered on a separate lesion.

Composite plans should be generated to account for normal tissue dose from each lesion that is treated. Dose summation from multiple treatment sites should be determined on a single CT scan that encompasses the relevant anatomic region. A planning CT dataset that includes all targets and relevant critical structures in the imaging study should be obtained when possible. When this is not possible due to the size of the imaging study, CT datasets should be divided into two parts and treatment fields should be adjusted

so that dose spillage from the treatment of targets in one dataset to the next is minimal such that the dose contributions do not require summation.

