### **6.4 Definition of DLT**

Dose-limiting toxicities (DLTs) will be evaluated during the continuous toxicity monitoring component of the trial. The period for evaluating DLTs will be from the time of first administration of durvalumab until completion of the continuous toxicity monitoring of the first 20 enrolled subjects who have been followed for four weeks after the last dose of radiation. Subjects who do not remain on the study up to this time for reasons other than DLT will be replaced with another subject. Grading of DLTs will follow the guidelines provided in the Common Terminology Criteria for Adverse Events (CTCAE) version 4.03.

A DLT will be defined as any Grade 3 or higher toxicity that occurs during the DLT evaluation period which is from the time of first administration of durvalumab until four weeks after the last dose of radiation. Toxicity that is clearly and directly related to the primary disease or to another etiology is excluded from this definition. The following will be DLTs:

- Any Grade 4 irAE
- Any  $\geq$  Grade 3 colitis
- Any Grade 3 or 4 noninfectious pneumonitis irrespective of duration
- Any Grade 2 pneumonitis that does not resolve to  $\leq$ Grade 1 within 3 days of the initiation of maximal supportive care
- Any Grade 3 irAE, excluding colitis or pneumonitis, that does not downgrade to Grade 2 within 3 days after onset of the event despite optimal medical management including systemic corticosteroids or does not downgrade to  $\leq$ Grade 1 or baseline within 14 days
- Liver transaminase elevation  $> 8 \times$  ULN or total bilirubin  $> 5 \times$  ULN

- Any  $\geq$ Grade 3 non-irAE, except for the exclusions listed below

The definition excludes the following conditions:

- Grade 3 fatigue lasting  $\leq$  7 days
- Grade 3 endocrine disorder (thyroid, pituitary, and/or adrenal insufficiency) that is managed with or without systemic corticosteroid therapy and/or hormone replacement therapy and the subject is asymptomatic
- Grade 3 inflammatory reaction attributed to a local antitumor response (e.g., inflammatory reaction at sites of metastatic disease, lymph nodes, etc). These inflammatory reactions must be specific to a tumor-bearing organ and must respond to steroids.
- Concurrent vitiligo or alopecia of any AE grade
- Grade 3 infusion-related reaction (first occurrence and in the absence of steroid prophylaxis) that resolves within 6 hours with appropriate clinical management

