### **6.5.2 Radiation therapy toxicity evaluation and management**

Acute radiation toxicities are those that occur within 90 days from therapy start and will be graded according to CTCAE v4.03. Toxicities related to RT differ based on the location of the treated lesion(s) and are related to dose received by OARs near the targeted lesion. The majority of lesions that receive ER on this study are anticipated to be in the thorax and abdomen based on the patterns of spread of pancreatic cancer. The most common sites of distant metastases are the liver, abdominal peritoneum, and lungs. Accordingly, the most likely potential acute radiation adverse events include fatigue, dermatitis, pneumonitis, esophagitis, colitis, hepatitis, nausea, vomiting, anorexia, and diarrhea.

RT should be continued without interruption, if possible. Grade 3 or higher acute toxicity from RT is not expected and is not expected to lead to RT interruption. However, Grade 3 or higher acute toxicity may necessitate a treatment break. If a treatment delay for acute toxicity is required, the total radiation dose and dose per fraction will not be modified. Any missed radiation fractions should be made up as quickly as possible; if needing to give RT and durvalumab on the same day then the RT should be given first, if possible. It should be noted that any Grade 3-5 acute radiation toxicity counts toward the early stopping rule.

Patients will be evaluated by a radiation oncologist at least once weekly during RT (Weeks 2 and 4) for physical examination and toxicity evaluation. Patients will be seen at least every 4 weeks by a radiation oncologist or medical oncologist thereafter starting in Week 8.

Late toxicities are those that occur after 90 days of therapy start and will be graded according to CTCAE v4.03. Late toxicities, like acute toxicities, are related to dose received by OARs near the targeted lesion.

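### The 20-patient toxicity stopping rule has no single definition of which events count and until when: Sections 11.2.1, 6.4 and 6.5.2 give windows ending at about Day 45, Day 59 and Day 91 or 105

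*Combined protocol and SAP*

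**What the plan says.** Four places describe the same monitoring of the first 20 patients.

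- **Section 11.2.1.** The endpoint is Grade 3-5 acute non-hematologic toxicity, judged against the printed Pocock boundary b_k. The window for observing early toxicity "is pragmatically defined as the time during and within two weeks after the completion of RT". The synopsis has the same window ("pragmatically defined as the time during and within 2 weeks after the completion of RT"), and Section 3.3 repeats it.
- **Section 5.2.2.** "RT is scheduled to be delivered daily on Days 15-17 and Days 29-31". The last fraction therefore falls on Day 31.
- **Section 6.5.2.** "Acute radiation toxicities are those that occur within 90 days from therapy start". The section does not say whether therapy means durvalumab or radiotherapy. It then adds: "It should be noted that any Grade 3-5 acute radiation toxicity counts toward the early stopping rule". It also says: "Grade 3 or higher acute toxicity from RT is not expected and is not expected to lead to RT interruption".
- **Section 6.4.** Dose-limiting toxicities (DLTs) are evaluated within the monitoring component, from the first durvalumab dose to four weeks after the last radiation dose. The section refers to "continuous toxicity monitoring of the first 20 enrolled subjects who have been followed for four weeks after the last dose of radiation". It has its own lists of inclusions and exclusions.

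The synopsis and Section 11.2.1 close the component once 20 patients have been enrolled and have finished treatment without a crossing. Both give the stopping probability as 4.9% at a true rate of 10%, and as above 99% at 50% or more.

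**The concern.** A boundary of this kind needs a yes-or-no outcome for each patient, and that requires one event definition and one period in which it can occur. The sections do not agree on either. A Grade 3 radiation toxicity on Day 60 counts under Section 6.5.2. Under Section 11.2.1, if its window is the counting window, the same event comes too late. No section is given precedence.

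This is the only formal early-stopping rule in the protocol; a futility rule is expressly not planned. It protects patients receiving a combination whose safety profile the synopsis calls unknown. A crossing stops the trial and ends treatment for everyone then on it. Because b_k lies between 2 and 6, a single disputed patient can decide the outcome. The 4.9% figure is also conditional on a per-patient rate of 10%, and that rate has a definite meaning only once the event and the window are fixed.

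**Working it through.** **Window ends.** Inputs: durvalumab starts on Day 1; radiotherapy is given on Days 15-17 and 29-31 (Section 5.2.2). Each end is taken as start day plus length.

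| Section | Countable event | Window end |
|---|---|---|
| 11.2.1, 3.3, synopsis | Grade 3-5 acute toxicity, non-hematologic in 11.2.1 and the synopsis | 31 + 14 = Day 45 |
| 6.4 | DLT by its own list; link to b_k not stated | 31 + 28 = Day 59 |
| 6.5.2, from durvalumab | any Grade 3-5 acute radiation toxicity | 1 + 90 = Day 91 |
| 6.5.2, from radiotherapy | the same | 15 + 90 = Day 105 |

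Section 6.5.2 therefore runs 91 - 45 = 46 days or 105 - 45 = 60 days past Section 11.2.1. The starts differ too: read literally, the window in 11.2.1 opens with radiotherapy on Day 15, whereas that in 6.4 opens on Day 1.

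**Event lists, 6.4 against 11.2.1.** Neither contains the other. A Grade 2 pneumonitis that does not settle within three days is a DLT but is not Grade 3-5. Grade 3 fatigue lasting no more than seven days is Grade 3 and non-hematologic but is excluded as a DLT.

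**The plan's own stopping probabilities.** The printed boundary is: none at k = 1; 2 at k = 2; 3 at k = 3-6; 4 at k = 7-12; 5 at k = 13-17; 6 at k = 18-20. Let f_k(x) be the probability of x events among k patients with no stop so far. Then f_k(x) = (1 - p) f_{k-1}(x) + p f_{k-1}(x - 1). Any mass that reaches b_k is removed and added to P(stop).

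First steps at p = 0.10:
- k = 2: stop with probability 0.1 × 0.1 = 0.0100. This leaves f_2(1) = 2 × 0.1 × 0.9 = 0.18.
- k = 3: three events are impossible without an earlier stop, so nothing is added. f_3(2) = 0.1 × 0.18 = 0.018.
- k = 4: stop with probability 0.1 × 0.018 = 0.0018.

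Continued to k = 20:

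| True rate p | P(stop), recomputed | P(stop), stated |
|---|---|---|
| 0.10 | 0.0488 | 4.9% |
| 0.12 | 0.0837 | not given |
| 0.15 | 0.1575 | not given |
| 0.50 | 0.9878 | above 99% |

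The 4.9% reproduces. The figure at 50% does not quite: it is 98.8%, and 99% is reached at p = 0.509.

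**Sensitivity to the reading (illustration).** Suppose 10% of patients have an event under Section 11.2.1 and a further x have one countable only under Section 6.5.2. The documents give no x, so a range is assumed.

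| x | Rate under the wider reading | P(stop) | Difference from 4.9% |
|---|---|---|---|
| 0 | 10% | 4.9% | 0 |
| 2 points | 12% | 8.4% | 0.0837 - 0.0488 = 3.5 points |
| 5 points | 15% | 15.8% | 0.1575 - 0.0488 = 10.9 points |

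In this illustration every event under the narrower reading also counts under the wider one. The last column is therefore also the proportion of trials in which the two readings lead to different stop-or-continue decisions. The calculation takes outcomes as known in order of entry.

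**The case against.** The strongest reply is that the two-week phrase does not limit what may be counted. It stands in the sentence that justifies staggered entry, and may say only when a patient's outcome is treated as observed for accrual. The endpoint sentence says acute without a day limit, Section 6.5.2 supplies a meaning of acute for radiation toxicity, and the component stays open until 20 patients have finished treatment. On that view 6.5.2 completes 11.2.1. This reading is possible, and for that reason it would be too strong to say that 11.2.1 certainly excludes a Day 60 event. It does not settle the matter, though. If the two-week period is not the counting window, 11.2.1 states none. The 90 days still have no start date, and the role of DLTs is still unstated.

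The second reply concerns size. Section 6.5.2 does not expect Grade 3 or higher acute radiation toxicity, which corresponds to the zero row. Late events under staggered entry might also be scored when more patients are in the denominator, and with a benchmark median PFS of 3 months some patients would progress before Day 91 or 105. This stands: the non-zero rows show sensitivity and do not estimate an effect.

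The six-patient cap on active treatment, committee oversight and continuing adverse event recording do limit exposure. None of them says which events count.

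**Conclusion.** The inconsistency is established from the text. The window ends at about Day 45, Day 59, or Day 91 or 105 depending on the section, the event definitions differ, and nothing ranks them. As written, the rule cannot be applied in one agreed way. It should be fixed. Confidence is high on the inconsistency; its practical effect is unknown, from none upward, and the 8.4% and 15.8% rest on the assumed 2 and 5 points.

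Three stronger inferences are not supported:
- *The boundary is miscalibrated.* The 4.9% reproduces from the printed boundary. What is missing is confirmation that the 10% null belongs to the chosen event and window.
- *The longer window would greatly raise stopping.* Extrapolating a constant hazard from 10% at Day 45 gives 1 - 0.9^(90/44) = 19.4% by Day 91 and P(stop) of about 30%. The documents give no event-time distribution, and the later events in 6.5.2 are radiation toxicities only, which it does not expect at this grade.
- *Hematologic events count, or no adverse event assessment covers the gap before Week 8.* The omission of non-hematologic in Section 3.3 is probably shorthand, since the synopsis, 3.1 and 11.2.1 all carry the restriction. The blank cell in the adverse event row of the main schedule may be an extraction fault, and Section 10.3.1 has events recorded throughout treatment.

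The figure above 99% at a 50% rate is a separate, minor misstatement that changes no decision.

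**What to change.** - Reconcile Sections 3.3, 6.4, 6.5.2 and 11.2.1 and the synopsis so that the stopping rule has one event definition and one counting window, with its start and end named. Any 90-day period that is kept needs a stated start date. Which events and which window apply is the sponsor's clinical decision.
- If the two-week period is meant only for accrual, say so and state the counting window separately.
- State whether DLTs under Section 6.4 count against b_k. If they do not, 6.4 can keep its own list and window.
- Confirm that the 10% null rate refers to the chosen event over the chosen window.
- In the synopsis and Section 11.2.1, change the stopping probability at a 50% rate to 98.8%, or to about 99%.

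The cost is amendment wording in four sections and the synopsis, and one probability in two places. The sample size is unaffected. The boundary stays as printed unless the sponsor finds that the 10% null does not fit the chosen event and window.

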The chosen design parameters for the continuous toxicity monitoring portion of the trial have been chosen to give a high probability of stopping the study in case of unexpectedly high risk of toxicity.

The probability of early stopping is 4.9% if the true incidence of G3+ toxicity is 10%; the probability of early stopping is >99% if the true incidence of G3+ toxicity is 50% or more.

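### The stated stopping probability of more than 99% at a 50% toxicity rate is 98.8% under the printed boundary, and no figure is given between 10% and 50%

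*Combined protocol and SAP*

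**What the plan says.** Section 11.2.1 sets the scope of the rule: "Continuous toxicity monitoring will occur for the first 20 patients enrolled". Its Table 1 prints the values of b_k and is captioned "Pocock boundary for early stopping due to grade 3+ toxicity with a probability of stopping of about" 0.05 at a reference rate of 0.1. The same table appears in the synopsis and in section 3.3. The stated aim is "keeping the probability of early stopping at around 5% if the true underlying rate of this toxicity is 10" percent.

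Two operating points follow, in the synopsis and again in section 11.2.1. The first is a 4.9% chance of stopping at a true rate of 10%. For the second, section 11.2.1 says that "the probability of early stopping is >99" percent from a true rate of 50% upwards; in the synopsis the full clause reads "the probability of early stopping is >99% if the true incidence of G3+ toxicity is 50% or more". The sentence before them says that the parameters were "chosen to give a high probability of stopping the study in case of unexpectedly high risk of toxicity". No stopping probability is given for any rate between 10% and 50%, and the plan does not define what rate counts as unexpectedly high.

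If 20 patients complete therapy without a crossing, "the continuous toxicity monitoring component will be concluded and the outcome will be reported"; accrual then continues to 39, with toxicity recorded and reported for the whole cohort.

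**The concern.** The second operating point is a strict inequality attached to a named rate, and it can be checked exactly from the printed table. It fails at the rate it names. The error is small, but it appears twice in a description of how the safety rule performs.

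The more useful question is what a reader takes from the two points together. They lie at the reference rate and at five times that rate. Shown only 4.9% and more than 99%, next to a sentence about a high probability of stopping, a reader cannot see how the rule behaves at two or three times the reference. The risk is one of interpretation: completing 20 patients without a crossing could be taken as stronger reassurance about the combination than the rule provides.

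**Working it through.** **Inputs**, all from section 11.2.1:
- b_k for k = 1 to 20: none, 2, 3, 3, 3, 3, 4, 4, 4, 4, 4, 4, 5, 5, 5, 5, 5, 6, 6, 6.
- Rule: stop if the number of grade 3 or higher toxicities among the first k patients is at least b_k.
- Outcomes are independent with common rate p, with one look after each patient. This is the plan's own idealisation: "Ideally, the design assumes that the outcome, i.e. the incidence of G3+ toxicity among the first" *i* patients is known before patient *i*+1 enters.

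**Method.** Count the outcome sequences that never reach the boundary. Let N_k(x) be the number of sequences of length k with x toxicities that have not stopped. Start with N_0(0) = 1, apply

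N_k(x) = N_{k−1}(x) + N_{k−1}(x−1),

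and set N_k(x) = 0 whenever x ≥ b_k. Counts for x = 0, 1, 2, …:

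| k | surviving sequences |
|---|---|
| 6 | 1, 6, 14 |
| 12 | 1, 12, 65, 194 |
| 17 | 1, 17, 135, 649, 1745 |
| 20 | 1, 20, 189, 1106, 4114, 7317 |

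Then P(stop) = 1 − Σ N_20(x) p^x (1−p)^(20−x), summed over x = 0 to 5.

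**Step 1: the plan's figure at 10%.** The six terms are 0.1216, 0.2702, 0.2837, 0.1844, 0.0762 and 0.0151. They sum to 0.9512, so P(stop) = 0.0488. This rounds to the stated 4.9% and confirms the reading of the table and rule.

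**Step 2: the plan's figure at 50%.** All 2^20 = 1,048,576 sequences are equally likely. The survivors number 1 + 20 + 189 + 1106 + 4114 + 7317 = 12,747. So P(stop) = 1 − 12,747/1,048,576 = 1 − 0.0122 = 0.9878. A value above 99% would need at most 10,485 survivors (1% of 1,048,576). A simulation of 1,000,000 trials gave 0.9878 at 50% and 0.0486 at 10%.

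**Step 3: where 99% is reached.** Solving P(stop) = 0.99 gives p = 0.509. The probability is 0.9903 at 51% and 0.9964 at 55%.

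**Step 4: other readings of the rule.**

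| Reading | at 10% | at 50% |
|---|---|---|
| Count reaches b_k (as above) | 4.9% | 98.8% |
| Count must exceed b_k | 0.8% | 95.8% |
| One look at patient 20 only | 1.1% | 97.9% |

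Neither alternative gives 99% at 50%, and both lose the 4.9%. Shifting any one b_k by 1 so that the 50% value exceeds 99% raises the 10% value to at least 5.7%. A misprint in a single table entry therefore does not explain the figure.

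**Step 5: rates the plan does not report.**

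| True rate | P(stop within 20) | P(no crossing) |
|---|---|---|
| 15% | 15.8% | 84.2% |
| 20% | 32.8% | 67.2% |
| 25% | 52.3% | 47.7% |
| 30% | 70.0% | 30.0% |
| 40% | 91.9% | 8.1% |

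**The case against.** The strongest reply is that the only false statement is out by about 0.2 points. The sentence fails only for true rates from 50% to about 50.9%; above that it is correct. No boundary value, sample size or decision depends on it, and about 99% would have been accurate. That stands, and it sets the severity.

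A reader might go further and infer that the plan promises a high chance of stopping at two or three times the reference rate, and breaks that promise. The documents do not support this. The phrase about high probability is tied to an undefined level of risk, and the only high rate quantified is 50% or more. Nor do they name 20% to 30% as the expected excess: section 1.2.2 reports 9.4% treatment-related grade 3 or higher events with durvalumab alone, and section 6.5.2 does not expect grade 3 or higher acute radiation toxicity. Sections 1.4 and 1.5 do raise the possibility of added toxicity from the combination, but give no rate. The intermediate values are therefore unreported context and not a second error.

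A reader might also infer that safety monitoring ends at patient 20. Only the formal numerical boundary ends there. Toxicity is still recorded and reported for the whole cohort (section 11.2.1), the DSMC/QAC oversees the trial (section 13.1.2), and the durvalumab supplier's ongoing safety monitoring continues (section 14.2).

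**Conclusion.** The figure is wrong as written, by a small margin: 98.8% at a 50% rate against a stated value above 99%. The 4.9% at 10% is right. This is a low-severity correction of text in two places, and it does not call the boundary or the design into question.

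The accompanying sentence about high probability needs qualifying. At a true rate of 20% the rule is not crossed about two times in three, and at 30% about three times in ten. Twenty patients without a crossing would therefore not exclude a doubling or tripling of the reference rate.

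The figures assume independent outcomes at a constant rate, each known before the next patient enters. The plan permits staggered entry with up to 6 patients on active treatment during monitoring, which could delay the moment a crossing is seen. That is not modelled here.

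**What to change.** In the synopsis and in section 11.2.1, replace the figure of more than 99% with 98.8% (or about 99%) at a true rate of 50%. In both places, qualify the sentence on high probability with the exact stopping probabilities: 33% at 20%, 52% at 25%, 70% at 30% and 92% at 40%. State that they assume fully sequential outcomes, and that a completed monitoring phase without a crossing does not exclude a two- to three-fold excess over the 10% reference.

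The cost is an edit to two paragraphs. The boundary, sample size and data collection are unchanged, and no new stopping boundary for patients 21 to 39 is proposed.
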